This Statistical analysis plan (SAP) compares postoperative rehabilitation outcomes between an experimental training group (n=16) and a control group (n=16) across three key timepoints: immediate post-surgical baseline (0-1 week), mid-intervention (4-5 weeks), and post-intervention (8-9 weeks). The study employs a repeated measures design to evaluate five primary outcome domains: muscle size (continuous, cm), range of motion (continuous, degrees), muscle strength (ordinal, 0-5 scale), pain perception (ordinal, VAS 0-10), and joint effusion (ordinal, 0-3 clinical scale).

In contrast, This SAP includes descriptive statistics, normality assessments, inferential statistical tests with corresponding assumptions, multiple comparison adjustments, missing data handling procedures, and software implementation to ensure reproducibility.

1. Descriptive Statistical Approaches

Comprehensive descriptive analyses will precede all inferential testing to characterize the dataset and inform appropriate test selection. For continuous variables (muscle size, ROM), we will report means with standard deviations (SD) for normally distributed data and medians with interquartile ranges (IQR) and full ranges for non-normal distributions, supplemented by graphical representations including boxplots with superimposed individual data points to visualize both group trends and individual trajectories. Ordinal variables (strength, pain, effusion) will be summarized using median scores with IQRs and frequency distribution tables showing counts/proportions at each ordinal level, with stacked bar charts employed to visualize proportional changes across timepoints. These descriptive analyses will be stratified by group (experimental vs control) and timepoint to enable preliminary assessment of intervention effects and data distributions prior to formal hypothesis testing.

2. Data Characteristics and Variable Classification

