The dataset comprises both continuous and ordinal variables requiring distinct analytical approaches. Continuous variables including muscle circumference (measured via standardized tape measure protocol) and active range of motion (measured via goniometry by blinded assessors) will be analyzed for both central tendency and variability. Ordinal variables including manual muscle testing scores (Medical Research Council 0-5 scale), visual analog pain scores (recorded as integers 0-10), and clinician-rated effusion scales (0=none, 3=severe) will be analyzed using non-parametric methods due to their inherent rank-based properties and expected non-normal distributions. All variables will be assessed at three protocol-specified timepoints with identical measurement protocols maintained across groups to ensure comparability.

3. Normality and Parametric Assumption Testing

Formal statistical testing for normality assumptions will be conducted for all continuous variables prior to selecting inferential methods. The Shapiro-Wilk test ($\alpha=0.05$) will be applied to residuals from all continuous outcome measures within each group-by-time combination, supplemented by visual inspection of Q-Q plots and histograms to detect deviations from normality that may not reach statistical significance in small samples. Homogeneity of variance between groups will be verified using Levene's test for equality of variances when parametric between-group comparisons are planned. For instances where normality or homogeneity assumptions are violated (Shapiro-Wilk $p\leq0.05$ or Levene's $p\leq0.05$), pre-specified non-parametric alternatives will be implemented as detailed in subsequent sections. All assumption testing results will be documented in supplementary materials to demonstrate the appropriateness of selected analytical methods.

4. Primary Inferential Statistical Methods

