4.1 Within-Group Longitudinal Analyses

For evaluating changes over time within each experimental arm, distinct approaches will

be employed based on variable characteristics. Continuous variables meeting normality assumptions will be analyzed using repeated measures ANOVA with Greenhouse-Geisser correction for sphericity violations, followed by paired t-tests with Bonferroni-adjusted α levels for post-hoc timepoint comparisons when omnibus tests reach significance. Non-normal continuous data and all ordinal outcomes will utilize the Friedman test (non-parametric equivalent to repeated measures ANOVA) followed by Wilcoxon signed-rank tests for post-hoc comparisons with appropriate multiplicity adjustments. Effect sizes will be reported as Cohen's d for parametric analyses and rank-biserial correlations for non-parametric tests to quantify the magnitude of observed changes independent of sample size considerations.

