4.2 Between-Group Comparative Analyses

Experimental versus control group comparisons at each timepoint will employ independent samples t-tests for normally distributed continuous variables with equal variances, Welch's t-tests for unequal variances (as determined by Levene's test), and Mann-Whitney U tests for non-normal continuous or ordinal data. Between-group effect sizes will be reported as mean differences with 95% confidence intervals for parametric tests and Hodges-Lehmann median differences for non-parametric analyses. To account for baseline imbalances in this pilot study, exploratory analyses of covariance (ANCOVA) may be conducted for continuous outcomes using baseline measurements as covariates if substantial pre-intervention group differences are detected despite randomization.

5. Missing Data Handling Protocol

Missing data patterns will be formally evaluated using Little's MCAR test prior to primary analyses. Given the pilot nature of this study with limited sample size, primary analyses will employ complete case approaches with explicit reporting of missing data proportions by group and timepoint. Sensitivity analyses will compare complete case results with multiple imputation approaches using chained equations (MICE)

incorporating baseline characteristics and observed follow-up data as predictors. Participants with missing baseline data will be excluded from all analyses, while those missing later timepoints will be retained for analyses where their available data permits. A participant flow diagram will document attrition at each study phase.

6. Software Implementation and Reproducibility

All analyses will be conducted using Stata MP 18.0. Graphical outputs will adhere to STROND guidelines for transparent reporting of non-normal data distributions.

Reference:

Ardern, C. L., Webster, K. E., Taylor, N. F., & Feller, J. A. (2011). Return to sport following anterior cruciate ligament reconstruction surgery: A systematic review and meta-analysis of the state of play. *British Journal of Sports Medicine*, 45(7), 596–606. <https://doi.org/10.1136/bjsm.2010.076364>

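### The main between-arm tests leave out a baseline that is measured for all five outcomes, and the only adjusted analysis is optional, exploratory and tied to an undefined imbalance

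*Combined protocol and SAP*

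**What the plan says.** SAP section 4.2 sets out the comparison between arms: "Experimental versus control group comparisons at each timepoint will employ independent samples t-tests for normally distributed continuous variables with equal variances". Welch's test is used for unequal variances, and Mann-Whitney for non-normal or ordinal data. Effects are reported as mean differences with 95% confidence intervals, or as "Hodges-Lehmann median differences for non-parametric analyses". None of these uses baseline.

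The one route to adjustment is that "exploratory analyses of covariance (ANCOVA) may be conducted for continuous outcomes using baseline measurements as covariates if substantial pre-intervention group differences are detected". The SAP's opening paragraph classes only muscle size and ROM as continuous, so strength, pain and effusion have no baseline-adjusted comparison. No threshold defines a substantial difference, and nothing says that ANCOVA would then replace the t-test.

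Baseline is available for every outcome. SAP section 2 states: "All variables will be assessed at three protocol-specified timepoints", and the first timepoint is baseline. SAP section 5 states: "Participants with missing baseline data will be excluded from all analyses". The repeated-measures methods of section 4.1 do use baseline, but only "For evaluating changes over time within each experimental arm", so they do not compare the arms.

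**The concern.** The plan requires a baseline from every analysed participant and then leaves it out of the main comparison. With 16 per arm precision is scarce, and the baseline value of the same measurement is an obvious covariate.

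The conditional clause does not repair this. It makes adjustment depend on an imbalance judged after the data are in, with no rule for judging it and no statement of which result would be the main one. Read literally, testing at each timepoint also means that 5 of the 15 comparisons (5 outcomes x 3 timepoints) are tests of randomised baselines, which say nothing about treatment.

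At stake are the width of the confidence intervals for circumference and ROM, the power of all five comparisons, and whether the analysis is fixed before results are known.

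**Working it through.** **The plan's own figure.** Study Design item 7 says that 32 participants rest on a power analysis, but gives no effect size, SD, alpha or power, so it cannot be reproduced. Worked backwards, 16 per arm gives 80% power for a difference of about 1.02 SD (t-test, two-sided 0.05).

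**Inputs.** From the documents: 16 per arm (SAP opening paragraph). Assumed: two-sided 0.05, suggested by the 95% intervals; effect d in SD units; baseline-outcome correlation rho from 0 to 0.7.

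**Unadjusted test.** The noncentrality is d/sqrt(2/16). For d = 0.8 this is 0.8/0.3536 = 2.26 on 30 df, giving 59.1% power.

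**Ordinary ANCOVA.** Relative to the t-test, the variance is multiplied on average by (1 - rho^2) x (1 + 1/28), with 29 df:
- rho 0.3: 0.91 x 1.036 = 0.943, SE ratio 0.97
- rho 0.5: 0.75 x 1.036 = 0.777, SE ratio 0.88
- rho 0.7: 0.51 x 1.036 = 0.528, SE ratio 0.73

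Break-even on variance is rho^2 = 1 - 28/29, so rho = 0.186; on interval half-width it is 0.193. Power below averages the noncentral t over the chance baseline imbalance.

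| | Unadjusted | rho 0 | rho 0.3 | rho 0.5 | rho 0.7 |
|---|---|---|---|---|---|
| Power, d = 0.5 | 28% | 27% | 29% | 34% | 47% |
| Power, d = 0.8 | 59% | 58% | 62% | 70% | 85% |
| Power, d = 1.0 | 78% | 77% | 80% | 87% | 96% |
| 95% CI half-width (SD) | 0.72 | 0.74 | 0.70 | 0.64 | 0.53 |
| Power, d = 0.8, HC3 errors (simulated) | 59% | 54% | 57% | 66% | 83% |

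With HC3 errors, break-even moves to a little above rho 0.3. To match ordinary ANCOVA, an unadjusted test would need 16/0.943 = 17, 16/0.777 = 21 or 16/0.528 = 30 per arm at rho 0.3, 0.5 or 0.7.

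**Why robust errors.** Ordinary ANCOVA would give up the protection that Welch's test provides. The SAP has no dropout allowance, so the arms may end unequal. If the smaller arm has twice the SD (assumed), simulated type I error of ordinary ANCOVA is about 7.5% at 16 v 12 and a little over 9% at 16 v 10. Welch stays near 5%, and ANCOVA with HC3 errors is at 4.4 to 4.8%.

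**Does the existing trigger help?** Suppose that a substantial difference means a baseline test with p < 0.05, and that ANCOVA then replaces the t-test (both assumptions). Simulated power at d = 0.8 is 60% v 70% for always adjusting at rho 0.5, and 61% v 85% at rho 0.7. The trigger recovers almost none of the precision.

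**Validity.** Simulated type I error of the unadjusted t-test is 5.0% at every rho.

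**Ordinal outcomes.** Gain in power of rank ANCOVA (Quade) over Mann-Whitney, assuming a latent shift of 0.8 SD (20,000 runs per cell), in percentage points:

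| Score pattern | rho 0.3 | rho 0.5 | rho 0.7 |
|---|---|---|---|
| 3, 4 or 11 levels evenly used | 1.5-2 | 6-9 | 14-23 |
| Baseline clustered 80/15/5% | 1 | 4 | 7-9 |
| 95% of baseline scores on one level | 0 | 1 | 2 |

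**The case against.** The strongest defence is that the planned tests are valid, this is a pilot, and the benefit is unknown. Baseline is taken just after surgery and may predict week 8-9 status weakly, while ordinal baseline scores may cluster on one level. With HC3 errors the adjusted analysis has less power than the t-test until rho is a little above 0.3. For three of the five outcomes, the rank test adds a p-value but no adjusted estimate. All of this stands, and it limits the size of the claim. It does not justify leaving the choice open. The pilot label does not help either: the protocol's objective is to compare effectiveness, and an estimation study needs narrow intervals.

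Three stronger readings are tempting, and the documents do not support them:
- **That the unadjusted tests are biased or inflate type I error.** They do neither over randomisation. Among trials with a chance baseline gap above 0.5 SD (about 16% of trials at this size), the simulated false-positive rate is about 12% at rho 0.5 and 19% at rho 0.7. That is the same imprecision seen conditionally, and trials with small gaps offset it.
- **That the plan allows the better of two p-values to be reported.** Doing so would raise type I error to about 7.4% (rho 0.5) or 8.3% (rho 0.7). But the SAP labels ANCOVA exploratory and does not say that it replaces the main test, so this is a worst case and not the plan's error rate.
- **That the trial forfeits some 26 points of power.** That is the ordinary ANCOVA result at rho 0.7 and d = 0.8. Neither value is in the documents.

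**Conclusion.** The point holds as a matter of precision and pre-specification, not of validity. For circumference and ROM at d = 0.8, ANCOVA with HC3 errors changes power by about -5, -2, +7 and +24 points at rho 0, 0.3, 0.5 and 0.7 (from 54, 57, 66 and 83% against 59%). Ordinary ANCOVA would do better at equal arm sizes, but is exposed if attrition and unequal variances coincide. For the ordinal outcomes, the gain runs from nothing to about 23 points, depending on rho and on how the scores spread. Every figure rests on assumed d and rho, and the continuous power figures also assume normality. What does not rest on an assumption is that the trigger is undefined and that the ordinal outcomes have no adjusted comparison.

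**What to change.** 1. For circumference and ROM, make ANCOVA on the baseline value the main between-arm analysis at weeks 4-5 and 8-9, whatever the observed imbalance. Report the adjusted mean difference with a 95% interval from HC3 standard errors. This also frees the main analysis from the Levene rule, which the SAP states in two ways: section 3 sends cases to non-parametric tests "For instances where normality or homogeneity assumptions are violated", while section 4.2 sends unequal variances to Welch's test.
2. Delete the imbalance trigger and the significance tests of baseline. Keep the unadjusted t, Welch and Mann-Whitney results for circumference and ROM as sensitivity analyses.
3. For strength, pain and effusion, keep Mann-Whitney with the Hodges-Lehmann difference and add rank ANCOVA (Quade) as a supporting test. State that the reported difference is unadjusted.
4. Confirm that baseline precedes the first training session. The inclusion criteria admit patients up to 4 weeks after surgery, whereas the SAP puts baseline at 0-1 week after surgery. These must be reconciled before baseline becomes a required covariate.
5. Study Design items 7 and 8 describe enrolment as actual and report no adverse events in this trial, so the trial may be well advanced. If outcomes have been seen by arm, report the adjusted analysis alongside the planned one and label it post hoc.

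**Cost.** SAP wording and a few lines of Stata, with no new data and no participants lost beyond those already excluded for missing baseline. The statistical price is one degree of freedom plus the robust errors: about 5 points of power at d = 0.8 if rho is 0 (under 2 without the robust errors). The ordinal outcomes still have no adjusted estimate.

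### Complete case as the primary analysis leaves mid-visit data out of the 8–9 week arm comparison, which can be biased if dropout follows earlier outcomes differently by arm

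*Combined protocol and SAP*

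**What the plan says.** SAP section 5 cites the pilot setting and limited numbers, then states that "primary analyses will employ complete case approaches with explicit reporting of missing data proportions by group and timepoint". Later in the same section, anyone without a baseline value is dropped from every analysis. For the rest, the rule is that "those missing later timepoints will be retained for analyses where their available data permits". Multiple imputation by chained equations (MICE), using baseline and observed follow-up data, is planned as a sensitivity analysis only. The section opens with "Missing data patterns will be formally evaluated using Little's MCAR test prior to primary analyses", but attaches no consequence to the result.

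SAP section 4.2 handles the arm comparison visit by visit: "Experimental versus control group comparisons at each timepoint will employ independent samples t-tests", with Welch or Mann-Whitney versions where assumptions fail. ANCOVA on baseline is exploratory and conditional on a visible baseline imbalance. No joint longitudinal model between arms is planned.

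SAP section 4.1 analyses change within each arm by "repeated measures ANOVA with Greenhouse-Geisser correction for sphericity violations", or by the Friedman test for non-normal and ordinal data. Of the five primary domains, two are continuous (muscle size, range of motion) and three ordinal (strength, pain, effusion).

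**The concern.** A small sample argues against complete case rather than for it: with 16 per arm, each observed visit counts. Under the planned tests, the 4–5 week value of someone who misses the last visit is not used in the 8–9 week comparison, although it is the best available information on how that person was doing.

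The protocol's masking section says that participants know their arm. If people doing badly at 4–5 weeks left one arm more readily than the other, those remaining at 8–9 weeks would no longer be comparable between arms. An unadjusted completer test cannot correct for that. An analysis that uses the earlier values can, provided that missingness depends only on what was observed.

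Section 5 also describes two different analysis sets, complete case and available data, without saying which test uses which.

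**Working it through.** **Inputs.** From the documents: 16 per arm, three visits, separate tests at each visit. Not in the documents: dropout, between-visit correlations, SDs and the expected effect. The protocol's enrolment item mentions a power analysis but gives none of its inputs, so there is no planned figure to reproduce. All values below for these quantities are assumptions.

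**1. Who is counted.** Let a fraction q miss each follow-up visit, independently.
- Tests needing all three visits (repeated measures ANOVA and Friedman in their usual form) lose 1 − (1 − q)². For q = 5%, 10%, 15% this is 1 − 0.9025 = 10%, 1 − 0.81 = 19%, 1 − 0.7225 = 28%.
- The 8–9 week arm comparison on available data loses only q.
- At q = 10%, strict complete case keeps 32 × 0.81 = 25.9. Available data at the final visit keeps 32 × 0.90 = 28.8. A model using any post-baseline visit keeps 32 × (1 − 0.01) = 31.7.

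**2. Which mechanisms bias the completer difference.** Large-sample simulation: SD 1, all visit correlations 0.6, true differences 0.25 (mid) and 0.50 (final), roughly 20% average dropout at the final visit. Outcome-driven dropout had logit −1.6 minus the outcome value. In the one-arm rows this applied to the experimental arm, with random 20% dropout in the control arm. In the opposite-directions row the sign was reversed in the control arm. The missing-at-random (MAR) estimate regresses the final value on baseline and mid-visit values within each arm. Bias is in SD units, with simulation noise of about 0.005:

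| Dropout at the final visit | Completers | Completer ANCOVA | MAR estimate |
|---|---|---|---|
| Completely at random | +0.002 | +0.002 | +0.004 |
| 10% vs 30%, by arm alone | −0.004 | −0.003 | −0.005 |
| On baseline, same in both arms | +0.001 | +0.001 | +0.001 |
| On mid-visit value, same in both arms | −0.014 | −0.006 | +0.001 |
| On baseline, one arm only | +0.100 | −0.005 | −0.006 |
| On mid-visit value, one arm only | +0.089 | +0.034 | −0.003 |
| On mid-visit value, opposite directions | +0.197 | +0.079 | −0.002 |
| On the unseen final value, one arm only | +0.125 | +0.079 | +0.070 |

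For correlations from 0.3 to 0.8, completer bias runs from +0.045 to +0.123 (mid-visit value, one arm) and from +0.099 to +0.264 (opposite directions).

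**3. Size at the trial's sample size.** 6,000 trials, 16 per arm, correlations 0.70 (baseline–mid), 0.60 (baseline–final), 0.75 (mid–final), true effects 0.40 and 0.80 SD, about 20% missing the final visit, control dropout driven by a poor mid-visit value. Over several assumed strengths of that dependence:
- completers: 0.58–0.66 SD, a shortfall of (0.80 − 0.66)/0.80 = 17.5% to (0.80 − 0.58)/0.80 = 27.5%;
- ANCOVA on completers: 0.70–0.73 SD;
- baseline-adjusted likelihood estimate: about 0.80 SD.

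With the same mechanism in both arms, completers give 0.797 and the likelihood estimate 0.798.

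**4. Precision.** In the same setting with data missing completely at random, the SEs are 0.394 (completer t-test), 0.325 (completer ANCOVA) and 0.315 (likelihood). Baseline adjustment alone supplies (0.394 − 0.325)/(0.394 − 0.315) = 87% of the gain. Check by formula with 16 × 0.8 = 12.8 completers per arm: √(2/12.8) = 0.395 for the t-test. With ANCOVA, 0.395 × √(1 − 0.60²) = 0.316, slightly below the simulated value because the slope is treated as known.

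Without treating baseline as a covariate, at a common correlation of 0.6, earlier visits explain R² = 2 × 0.36/1.6 = 0.45 of the final value. The likelihood SE is then √[2(0.45/16 + 0.55/12.8)] = 0.377, against 0.395 for completers (0.390 to 0.366 for correlations 0.3 to 0.8).

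**The case against.** Much can be said for the plan. It reports missingness by arm and visit, provides a flow diagram, and specifies MICE with observed follow-up data as predictors. MICE addresses the same missing-at-random mechanism, so a distorted completer result could come to light. The trial is a pilot, and a linear mixed model suits only two of its five primary domains. These points stand. They reduce the matter to which analysis is primary, but the plan does not say how a MICE result that disagreed would be read.

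A reader might infer three stronger things that the documents do not support.
- *Complete case is valid only if data are missing completely at random.* The first four rows of the table show otherwise: dropout by arm alone, or on outcome history in the same way in both arms, leaves the difference unbiased or nearly so.
- *The 10%, 19% and 28% losses apply to the arm difference.* They belong to the within-arm three-visit tests. The final-visit comparison loses only those absent at that visit, because section 5 retains the others.
- *The fall in SE from about 0.39 to 0.32 is the price of complete case.* Most of it comes from baseline adjustment, which ANCOVA on the same completers would give.

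Making MICE primary for the ordinal outcomes is also open to dispute, since the plan does not say how rank tests would be pooled across imputations.

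**Conclusion.** The point holds as a choice of primary analysis that can be improved cheaply; it does not show that the trial's result is biased. The planned 8–9 week comparison ignores the mid-visit data of those who leave, and its estimate can be wrong when dropout depends on earlier outcomes differently by arm. Open-label participation makes that possible; nothing in the documents shows that it happened.

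In the assumed adverse case, an effect of 0.80 SD is understated by about 18% to 28%. The exploratory ANCOVA, if run on completers, would remove only part of this. The direction is not fixed: selective dropout of poor responders from the experimental arm overstates the effect instead. Under symmetrical mechanisms there is little or no bias. The SE falls from about 0.38–0.39 to 0.32, mostly through baseline adjustment. These figures rest on assumed dropout, correlations and effects, and the likelihood estimate rests on missing-at-random. Under dropout driven by the unseen final value it was still biased, though less than completers (+0.07 against +0.13).

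The conflict in section 5 between complete case and available data needs correcting at any dropout rate.

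**What to change.** - **Muscle size and range of motion.** Make the primary arm comparison one mixed model for repeated measures, with arm, visit, arm-by-visit and baseline, a pre-specified covariance structure and small-sample degrees of freedom. Use all observed post-baseline visits, read off the 8–9 week difference, and report complete case as sensitivity.
- **Strength, pain and effusion.** Keep the planned rank tests on all participants observed at the visit, with MICE as the planned sensitivity analysis.
- **Analysis sets.** In section 5, replace complete case with the available-data set for each between-arm test, in line with the retention sentence. State that the within-arm three-visit tests use those with all three visits.
- **Discordance.** Add a sentence on how a MICE result that differs from the primary result will be interpreted.

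The cost is SAP wording and one model in the Stata package already named, with no new data collection. The downsides are that a covariance structure must be chosen with 32 patients and that the model relies on missing-at-random. The protocol lists enrolment as actual, so if outcomes have already been examined by arm, the change should be dated and labelled as made afterwards.

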Care Provider: Therapists administering interventions are unblinded.

None (Open Label): Not applicable; partial blinding is used.

6. Allocation

Participants are randomly assigned to BFR-RT or T-RT groups.

Method: Opaque envelopes with coded assignments prepared by an independent team member.

Stratification: Not specified, but typically balanced for age, sex, or baseline function.

7. Enrollment

- Target Sample Size: 32 participants.

Type: Actual (confirmed enrolled participants).

Justification: Based on power analysis to detect clinically significant differences in muscle hypertrophy/strength.

8. Additional Protocol Details

Intervention Protocol

Frequency: Biweekly sessions (16 total over 8 weeks).

BFR Technique:

- Occlusion band placed proximally on the affected limb.
- Tightness standardized to allow one finger beneath the band.

Standard Rehabilitation:

- Includes range of motion (ROM) exercises, strengthening, and functional training per hospital protocol.

Outcome Assessments

Time Points: Baseline (Week 0-1), Mid-Intervention (Week 4-5), Post-Intervention (Week 9).

Measures:

Primary: Muscle hypertrophy (ultrasound/MRI), strength (manual muscle testing).

Secondary: Pain (KOOS), knee ROM, effusion (circumference), adherence rates.

Safety Monitoring

- Adverse Events: Documented throughout; none reported in this trial.
- Exclusion Safeguards: No vascular pathologies or anticoagulant use.

9. Ethical Considerations

Informed Consent: Obtained from all participants.

Approval: Ethical approval was taken from the Institutional Review Board (IRB) of Rehman Medical Institute.

10. Participants:

- **Inclusion criteria:** Individuals who have undergone ACL reconstruction surgery within the past 4 weeks, free of any neurological impairments or significant cardiac, pulmonary, or metabolic conditions.
- **Exclusion criteria:** Individuals with contraindications to exercise, any other comorbidity, or systemic inflammatory conditions.

Outcome Measures:

- **Primary Outcome:** Muscle strength (measured using manual muscle technique). Muscle size (measured via measuring tape), ROM (Using goniometer), pain (using a Visual Analog Scale), and joint effusion (assessed clinically).

Statistical Analysis Plan

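### The rule excluding participants with missing baseline data from every analysis also drops them from follow-up comparisons and imputation that do not need an observed baseline

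*Combined protocol and SAP*

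**What the plan says.** SAP section 5 (Missing Data Handling Protocol) treats two kinds of gap differently within one sentence. For baseline: "Participants with missing baseline data will be excluded from all analyses". For follow-up: "those missing later timepoints will be retained for analyses where their available data permits". No reason is given for the difference. The same section says that "primary analyses will employ complete case approaches with explicit reporting of missing data proportions by group and timepoint", with multiple imputation by chained equations (MICE) as a sensitivity analysis.

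The analyses governed by this rule are in SAP section 4:

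- Between groups (4.2): "Experimental versus control group comparisons at each timepoint will employ independent samples t-tests", with Welch or Mann-Whitney tests as alternatives. None has a baseline term. Baseline enters only as an option: "exploratory analyses of covariance (ANCOVA) may be conducted for continuous outcomes using baseline measurements as covariates".
- Within groups (4.1): "Continuous variables meeting normality assumptions will be analyzed using repeated measures ANOVA", or the Friedman test, followed by paired comparisons between timepoints.

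The SAP introduction names five primary outcome domains and 16 participants per group.

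**The concern.** A participant with valid values at weeks 4-5 and 8-9 but no baseline value has everything that the follow-up between-group tests require. The rule discards that participant all the same, so these comparisons no longer use every randomised participant with data, and precision is lost where none needs to be.

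The phrase covering all analyses also takes in MICE. The sensitivity analysis would then start from the same reduced set as the complete-case analysis and could not show whether the exclusion mattered.

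The scope is also unclear. With five domains, the rule does not say whether a gap in one removes the participant from that outcome only or from all five. Two analysts could build different analysis sets from the same data.

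**Working it through.** **Step 1. Which analyses need an observed baseline?**

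| Analysis | Needs an observed baseline? |
|---|---|
| Between-group t, Welch or Mann-Whitney tests, weeks 4-5 and 8-9 (SAP 4.2) | No |
| Paired mid-versus-post contrast (SAP 4.1) | No |
| MICE sensitivity analysis (SAP 5) | No, it can impute it |
| Complete-case repeated-measures ANOVA or Friedman over three timepoints (SAP 4.1) | Yes |
| Paired contrasts involving baseline, and the baseline between-group comparison | Yes |
| ANCOVA without imputation (SAP 4.2, optional) | Yes |

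The exclusion is avoidable in the first three rows and unavoidable in the rest.

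**Step 2. The plan's own sample size.** The protocol (Enrollment) gives 32 participants and refers to a power analysis, but states no effect size, SD, alpha, power or dropout, so the figure cannot be reproduced. Assuming two-sided 0.05 and 80% power, the normal approximation for a difference of 1.0 SD gives n = 2 × (1.960 + 0.842)² / 1.0² = 15.7, or 16 per arm. So 32 fits an assumed difference of about 1 SD, which the documents do not state. By the t-test calculation, 16 per arm has 80% power at 1.02 SD.

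**Step 3. How many could be lost?** No missing-baseline rate is given. Let q be the assumed share missing in each of the five domains.

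- Gaps fully overlap: expected loss = 32 × q.
- Gaps independent, any gap excludes: expected loss = 32 × (1 − (1 − q)⁵).

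| q (assumed) | Full overlap | Independent gaps |
|---|---|---|
| 0% | 0 | 0 |
| 2% | 0.6 | 32 × 0.096 = 3.1 |
| 5% | 1.6 | 32 × 0.226 = 7.2 |
| 10% | 3.2 | 32 × 0.410 = 13.1 |

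If the rule is applied outcome by outcome, the expected loss for each outcome equals the full-overlap column.

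**Step 4. What a loss costs in the follow-up tests.** Two-sample t-test, two-sided 0.05 (assumed), equal loss in both arms (assumed). Power comes from the noncentral t distribution with noncentrality d × √(n/2) and 2n − 2 degrees of freedom, at d = 1.02 SD.

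| n per arm | Total lost | Power at 1.02 SD | Difference detectable with 80% power |
|---|---|---|---|
| 16 | 0 | 80% | 1.02 SD |
| 15 | 2 | 77% | 1.06 SD |
| 14 | 4 | 74% | 1.10 SD |
| 12 | 8 | 67% | 1.20 SD |

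At q = 5%, the full-overlap loss (1.6) is close to the second row, and the independent-gap loss (7.2) falls a little short of the last. These figures are for the t-test. The three ordinal outcomes use rank tests, so for them the table is only a guide.

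**The case against.** The strongest reply is that this may never matter. The five outcomes are simple bedside measures. If they are taken at one visit, gaps will tend to coincide, which puts the loss at the low end. Enrolment is listed as actual and no missing-baseline rate is reported, so the true loss may be nil. The within-group analyses do need baseline, so the exclusion is not pointless everywhere. All of this stands. It limits the size of the point but does not explain why someone with follow-up data should leave tests that use only follow-up data.

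Three stronger readings are tempting, and the documents do not support them.

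- *Any single gap removes the participant from all five outcomes.* That is one reading. The sentence could equally mean a missing baseline visit, or be meant outcome by outcome. It is an ambiguity, not a stated rule.
- *Exclusions will differ by arm.* Participants know their arm, and the documents do not say whether baseline precedes allocation. But SAP 4.2 links baseline measurements to group differences present before the intervention, so it treats baseline as pre-treatment. Arm-related exclusion is conjecture. If missingness is unrelated to arm, the rule costs precision without biasing the comparison.
- *The timing rules will exclude many.* The SAP introduction has an "immediate post-surgical baseline (0-1 week" window, while the protocol admits "Individuals who have undergone ACL reconstruction surgery within the past 4 weeks". A reader might infer that late entrants have no valid baseline. That needs weeks counted from surgery and late baselines counted as missing. No text says the latter, and the protocol's schedule (Week 0-1, Week 4-5, Week 9, around an 8-week programme) can be read as study weeks.

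**Conclusion.** The point holds in a limited form. As worded, SAP section 5 drops randomised participants from follow-up between-group tests, from the mid-versus-post paired contrast and from MICE, none of which requires an observed baseline.

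The size is unknown and may be zero. With 5% missing per domain (assumed), it ranges from about 2 to about 7 of 32, depending on how the gaps overlap and how the rule is read. Losing one per arm costs about 3 percentage points of power (80% to 77%) at 1.02 SD, under an assumed two-sided 0.05 and equal loss by arm.

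This is a needless loss of data, not evidence of bias between arms. The baseline window and the entry window need reconciling as a separate matter, and no exclusion count should be attributed to that inconsistency.

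**What to change.** Replace the baseline clause in SAP section 5 with wording such as: *A missing baseline value excludes a participant only from complete-case analyses of that outcome that use baseline. All other comparisons include the participant in the arm assigned, and the MICE analysis imputes the missing baseline.* This also settles the scope, because it works outcome by outcome. It fits the tests already planned and calls for no new model.

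The cost is one sentence and almost no extra analysis. The one drawback is that the number analysed will differ between analyses, so each table should state it by group. Because enrolment is listed as actual, date the change and report how many participants it affects, even if none.

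Separately, state the clock from which week 0-1 is counted, and reconcile the SAP's post-surgical baseline window with the entry window of up to 4 weeks after surgery.
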